## **Procedures Involved in the Human Research**

Screening and recruitment will be ongoing through January 2023. Participants will complete a baseline assessment with the research assistant prior to engaging in the decision support intervention. During the study period, participants will engage in the experimental decision support intervention and will maintain access to other services and supports normally available to them through the CSC program (e.g., medication, therapy). The PI will assess when the participant has determined what

decision they would like to work on with the decision coach via contact notes and supervision sessions. The PI will notify the research assistant when this determination has been made, and the research assistant will contact the participant at that time to have them complete the Decisional Conflict Scale a second time. Participants will not be offered additional payment for completing this measure at this time point. Upon completion of the intervention, participants will complete a post-intervention assessment with the research assistant. At post-intervention, participants will be asked to provide permission to audio-record responses to qualitative questions that are part of the qualitative assessment of decision-making needs and acceptability measure. Participants must provide permission to audio-record these portions of the research interview in order to participate in the study. At baseline and post-intervention, the study team will reach out to participants' psychiatrists/therapists in order to have them complete a questionnaire (Service Engagement Scale). A schedule of assessments collected at each time point is presented in Table 1.

	Table 1. Assessment Schedule		
	Baseline	During Intervention	Post-Intervention
Demographics/Clinical characteristics	X		
Multi-dimensional Scale of Perceived Social Support	X		X
Control Preference Scale	X		X
Perceived Involvement in Care Scale	X		X
Birchwood Insight Scale	X		X
Recovery Assessment Scale	X		X
Internalized Stigma of Mental Illness Scale	X		X
Empowerment Scale	X		X
Decision Self-Efficacy Scale	X		X
Service Use and Resource Form for Monthly Items	X		X

Brief Adherence Rating Scale	X		X
Intent to Attend Measure	X		X
Service Engagement Scale	X		X
Decisional Conflict Scale	X	X	X
Working Alliance Inventory	X		X
Intentional Peer Support Scale			X
Satisfaction with Decision Scale			X
Qualitative Measure of Decision-Making Needs			X
Acceptability Measure			X

Decision coaching, a process of non-directive support by a trained but neutral individual, is used to facilitate treatment decision-making through assessment of decision-making needs and delivery of specific intervention components to address them. These components may include facilitating access to information, clarifying values, helping a person obtain the needed support to make a decision, and screening for implementation barriers. Following standards of practice for decision coaching, the decision coach will evaluate individuals' decision-making needs and provide coaching tailored to these needs via telephone/videoconference or in face-to-face meetings. Individuals will be invited to speak with the decision coach as long and as many times as are necessary to make a treatment decision; however, it is expected that participation in the intervention will last approximately 3 months and it is suggested that individuals participate in the intervention on a weekly or biweekly basis. Participants will be asked to provide permission to audio record intervention meetings so that fidelity may be assessed. Participants may opt out of audio recording of intervention sessions and will still be able to participate in the intervention.

The research assistant will routinely administer an adverse events checklist at each study visit, and the decision coach will monitor for adverse events during each intervention meeting. If an adverse event occurs during a participant's participation in the study, the interventionist or research assistant will facilitate participants' access to prompt medical or professional care as appropriate, document the event on an adverse event reporting log, and immediately submit documentation of the event to the IRB and NIMH as appropriate.

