Service Use and Resources Form (SURF-M): SURF-M is a self-report measure that assesses service use over the past month from diverse sources of inpatient and outpatient care including antipsychotic medication with daily doses, and other psychotropic and non-psychotropic medication.

Brief Adherence Rating Scale (BARS): This scale assesses antipsychotic medication adherence of patients in outpatient settings.

Intent to Attend Measure: A measure that assesses participants' intention to engage in the coordinate specialty care program.

Service Engagement Scale: A clinician-rated scale that measures engagement in community mental health services.

Working Alliance Inventory: This 36-item scale assesses the strength of the therapeutic alliance with participants' therapists in three domains: agreement on goals, assignment of tasks, and the development of bonds.

Intentional Peer Support Scale: A scale designed to measure the relationship between the decision coach and patient.

Satisfaction with Decision Scale: This scale assesses a patient's satisfaction with a health care decision.

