## **f) Data Management**

Continuous and normally distributed variables will be summarized with means and standard deviations. Dichotomous variables will be summarized with frequencies and percentages.

To examine within-group differences in quantitative measures pre- and post-intervention, we will conduct paired samples t-tests.

Audio-recorded responses to qualitative questions about decision-making needs will be professionally transcribed verbatim. The research assistant and PI will analyze transcripts using the Constant Comparison Method. The parallel structure of the qualitative interview to the Decisional Conflict Scale will enable quantitative and qualitative data to be merged and reported through narrative weaving. Integration of these data will provide a more nuanced understanding of whether and how the intervention addresses decision-making needs than use of either type of data alone, and will be most informative for intervention refinement. Should quantitative and qualitative analyses yield discrepant findings, we will assess reasons for conflicting results (e.g., low power, question structure/content) and revise procedures accordingly.

Audio-recorded responses to qualitative acceptability questions will also be professionally transcribed verbatim. The research assistant and PI will analyze transcripts using the Constant Comparison Method. As open-ended questions do not parallel quantitative acceptability questions, acceptability data will be interpreted and reported contiguously.

Steps that will be taken to secure the data are described in the Privacy and Confidentiality section.

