## **g) Withdrawal of Subjects**

Participation is voluntary and there is no penalty if an individual chooses not to join the research study; their services will not be affected. If an individual enrolls in the study and later chooses to withdraw from the study, they may do so at any time without any penalty to them. They can simply withdraw from the study by telling the research staff in person when they are at study sites, or by contacting research staff by telephone or email.

Participants will be withdrawn from the study if they appear to be under the influence of alcohol or illegal drugs or are hostile to research staff. In such cases, they will not be paid for their time.

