## **12) Risks to Subjects**

During the research interviews and participation in the study intervention, topics may come up that are distressing or triggering, including diagnoses, symptoms, and negative treatment experiences. We will attempt to

minimize this risk by detailing what topics will be covered before participants begin the interview and intervention.

Participants may become fatigued or uncomfortable during research interviews. We will attempt to minimize these risks by allowing participants to schedule the remainder of the interview/assessment for another time, and by informing them that they may omit questions, or simply discontinue the interview/assessment, at any time.

In the event that a participant has been harmed by the research, we will facilitate prompt receipt of their psychiatric or medical care. However, participants will be responsible for the costs of such psychiatric or medical treatment, directly or through medical insurance and/or other forms of medical coverage. Temple University and research staff will not be responsible for the cost of this treatment. This has been made explicit on the informed consent forms.

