To examine within-group differences in quantitative decision-making targets pre- and post-intervention, we will conduct a paired samples t-test using DCS Factors Contributing to Uncertainty subscale scores. Responses to open-ended questions about decision-making targets will be analyzed qualitatively using the same procedure described previously. The parallel structure of the qualitative interview to the DCS will enable quantitative and qualitative data to be merged and reported through narrative weaving. Integration of these data will provide a more nuanced understanding of whether and how the intervention engages decision-making targets than use of either type of data alone, and will be most informative for intervention refinement. Should quantitative and qualitative analyses yield discrepant findings, we will assess reasons for conflicting results (e.g., low power, question structure/content) and revise procedures accordingly for the R01 study.

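### Could a refusal of audio-recording at the last visit cost the trial its quantitative post-intervention scores?

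*Combined protocol and SAP*

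**What the plan says.** Procedures Involved in the Human Research places the recording request at the final assessment: "At post-intervention, participants will be asked to provide permission to audio-record responses to qualitative questions". The next sentence makes it a condition: "Participants must provide permission to audio-record these portions of the research interview in order to participate in the study". The recording covers only the open-ended parts, namely the qualitative measure of decision-making needs and the qualitative acceptability items.

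For recordings of the coaching sessions, the same section does state the consequence of refusing: "Participants may opt out of audio recording of intervention sessions and will still be able to participate in the intervention".

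The analyses that need a post-intervention score are in section f) Data Management ("To examine within-group differences in quantitative measures pre- and post-intervention, we will conduct paired samples t-tests") and in the Statistical Analysis Plan ("we will conduct a paired samples t-test using DCS Factors Contributing to Uncertainty subscale scores").

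Two other sections bear on a late refusal. Section g) Withdrawal of Subjects gives the grounds on which staff remove a participant: "Participants will be withdrawn from the study if they appear to be under the influence of alcohol or illegal drugs", or hostility towards staff. Section 12) Risks to Subjects says participants will be told that "they may omit questions, or simply discontinue the interview/assessment, at any time".

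**The concern.** By the post-intervention visit a participant has completed the baseline assessment, the coaching and the mid-intervention DCS. A condition of participation that is raised only then has an awkward consequence if taken literally: someone who declines to be recorded no longer qualifies to be in the study, and the whole last visit could be lost. Most of that visit needs no recording.

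A paired t-test needs both scores, so such a person would drop out of the DCS test and the other before-after comparisons for a reason unrelated to whether the scales can be completed. Refusal might also be related to outcome, for example if people who gained little or were distressed are less willing to be recorded. The protocol gives an explicit rule for session recordings and none for the interview recording that feeds the primary endpoint. Neither document defines an analysis set or a missing-data rule to fall back on.

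**Working it through.** **1. What a literal reading would put at risk (Table 1).**
- Measures marked at post-intervention: 18.
- One is not collected from the participant. The Service Engagement Scale is described in section e) Study Endpoints as "A clinician-rated scale that measures engagement in community mental health services". That leaves 18 − 1 = 17.
- Two of the 17 have a recorded part (the qualitative needs measure and the acceptability measure). That leaves 17 − 2 = 15 scales with nothing to record: the DCS and 14 others.
- Measures with both a baseline and a post-intervention mark: 14, of which 14 − 1 = 13 come from the participant.

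The number of pairs actually lost depends on the reading. If refusal means removal from the study, the clinician rating would presumably not be sought either, and all 14 go. If the right to skip questions governs, none go. A loss of exactly 13 would require the visit to be cancelled while the clinician rating is still collected, and no section says that.

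**2. Which reading the documents support.**
- *The recording sentence* sets a condition for taking part. Applied to someone who has already taken part in everything else, it makes little sense as a new hurdle, but it makes sense as something agreed at entry. Section 17) Consent Process fits this: before consent, staff check that the person understands the tasks and how data are collected, and they read every form aloud. The consent form is not in the public copy, so its silence cannot be assumed.
- *Section g)* gives intoxication and hostility as grounds for removal by staff. Refusal of recording is not among them.
- *Section 12)* lets a participant skip any question. Someone who does not want to be recorded can skip the open-ended questions and complete the scales.
- *No section* says that completed quantitative scores are dropped for want of a recording.

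Taken together, these sections point to keeping the scales and losing only the open-ended responses.

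**3. Precision, if scores were lost anyway.** The planned sample is 20 (section 9). The documents give no refusal rate, so 1 or 2 late refusals are assumed. The half-width of the 95% confidence interval for mean change, in SDs of change, is t(0.975, n − 1)/√n:

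| n with a post score | Half-width | Increase over n = 20 |
|---|---|---|
| 20 | 0.468 | – |
| 19 | 0.482 | 3.0% |
| 18 | 0.497 | 6.3% |

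**4. Selective loss, if scores were lost anyway.** If a fraction f is lost and the refusers' mean change differs from the others' by δ SD, the completer mean differs from the full-sample mean by f × δ. Assume δ between 0.5 and 1.0:
- 1 of 20 lost: 0.05 × 0.5 = 0.025 to 0.05 × 1.0 = 0.05 SD.
- 2 of 20 lost: 0.10 × 0.5 = 0.05 to 0.10 × 1.0 = 0.10 SD.

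Even the largest of these is about a fifth of the half-width at n = 18 (0.10/0.497 = 0.20).

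**The case for a change.** The strongest case for a change is that the text really is silent. The request is timed at the last visit, the condition is worded as mandatory, and recording is not among the criteria in section b) Inclusion and Exclusion Criteria. The right to skip questions does not mention recording and does not expressly override the mandatory sentence. Even a condition agreed at entry leaves open what happens when someone later changes their mind. The protocol settled the same question for session recordings, and one or two sentences would settle it here.

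The silence stands, and so does the low cost of clarifying. Three further arguments carry less weight.

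- *Different programs might treat the same refusal differently.* The documents do not support this. Participants complete the post-intervention assessment with the research assistant, and section 9 provides for weekly staff meetings to resolve procedural issues. Program staff deliver the coaching and do not run this assessment.
- *The contrast with session recordings.* Those recordings serve fidelity assessment, so opting out costs no outcome data. The interview recording feeds the qualitative half of the primary endpoint, which is to be merged with the DCS. Requiring it firmly is a defensible design choice.
- *Refusal may not be random.* That is possible, but it matters only if the scores are discarded, and no section calls for that.

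**Conclusion.** No change to the plan is needed. The missing sentence is a gap that the study team can fill sensibly from the protocol's own text. Recording is most naturally an entry condition, refusing it is not a stated ground for removal, and participants may skip questions. A late refuser would therefore lose the open-ended responses and keep the quantitative scores.

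On that reading the paired analyses lose nothing. On the literal reading, with an assumed 1 or 2 refusals among 20, the interval for mean DCS change widens by about 3% or 6%. The mean could shift by 0.025 to 0.10 SD if refusers differ by an assumed 0.5 to 1.0 SD. Neither would alter what a single-group pilot of this size can conclude. The conclusion rests on late refusals being few, which the documents neither state nor contradict, and on the consent form, which is not in the public copy, not saying otherwise. If the protocol is being revised for another reason, a line saying when permission is obtained and that the scales are kept after a later refusal would be a reasonable courtesy, but the analysis does not depend on it.

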## **f) Data Management**

Continuous and normally distributed variables will be summarized with means and standard deviations. Dichotomous variables will be summarized with frequencies and percentages.

To examine within-group differences in quantitative measures pre- and post-intervention, we will conduct paired samples t-tests.

Audio-recorded responses to qualitative questions about decision-making needs will be professionally transcribed verbatim. The research assistant and PI will analyze transcripts using the Constant Comparison Method. The parallel structure of the qualitative interview to the Decisional Conflict Scale will enable quantitative and qualitative data to be merged and reported through narrative weaving. Integration of these data will provide a more nuanced understanding of whether and how the intervention addresses decision-making needs than use of either type of data alone, and will be most informative for intervention refinement. Should quantitative and qualitative analyses yield discrepant findings, we will assess reasons for conflicting results (e.g., low power, question structure/content) and revise procedures accordingly.

Audio-recorded responses to qualitative acceptability questions will also be professionally transcribed verbatim. The research assistant and PI will analyze transcripts using the Constant Comparison Method. As open-ended questions do not parallel quantitative acceptability questions, acceptability data will be interpreted and reported contiguously.

Steps that will be taken to secure the data are described in the Privacy and Confidentiality section.

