## **Study Protocol**

### **1) Abstract of the study**

The purpose of this research is to conduct a pilot study of a decision support intervention for young adults with early psychosis who are participating in early intervention services, also known as coordinated specialty care (CSC).

We will utilize a single-group, pre-post, convergent mixed methods design to explore whether and how the intervention addresses decision-making needs. The impact of the intervention on secondary outcomes (e.g., engagement in the program) will also be assessed. Additionally, we will evaluate the feasibility of research and intervention procedures, and the acceptability of information and support from the interventionist.

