### **2) Protocol Title**

Facilitating Emerging Adult Engagement in Evidence-Based Treatment for Early Psychosis through Peer-Delivered Decision Support Part 2

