### **e) Study Endpoints**

The primary endpoint is participants' treatment decision-making needs, as assessed by the Decisional Conflict Scale (DCS) and a qualitative measure designed to parallel items from the DCS.

We will also assess feasibility of study and intervention procedures by tracking data pertaining to recruitment, retention, and assessment procedures using CONSORT guidelines, and data related to implementation of the intervention (e.g., fidelity, number and duration of intervention meetings by participant, implementation barriers and facilitators). These data will be collected from fidelity checklists and contact notes completed by the decision coach.

Acceptability of the study intervention will be assessed via quantitative and qualitative questions about participants' level of satisfaction and experiences with the intervention. Exploratory, secondary outcomes/measures include:

Multidimensional Scale of Perceived Social Support: This scale assesses perceived adequacy of support in the following areas: family, friends, and significant other.

Control Preference Scale: This measure assesses patients' preferences for participation in treatment decision-making.

Perceived Involvement in Care Scale: This scale measures perceived clinician facilitation of patient involvement in decision-making, perceived level of information exchange between patient and provider, and perceived level of the patient's own involvement in medical decision-making.

Birchwood Insight Scale: A scale that measures dimensions of insight in the following areas: ability to re-label symptoms, awareness of mental illness, and recognition of a need for treatment.

Recovery Assessment Scale: This scale measures personal recovery and consists of 5 factors: personal confidence and hope, willingness to ask for help, goal and success orientation, reliance on others, and not being dominated by symptoms.

Internalized Stigma of Mental Illness Scale (ISMI): This measure is designed to assess individuals' experience of stigma related to mental illness.

Empowerment Scale: A scale that measures empowerment, control, self-determination, and decision making in the recovery process.

Decision-Self-Efficacy Scale: This measure assesses confidence in making an informed treatment choice.

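### Does the plan need to list the score analysed for each of the 13 secondary pre/post measures and name the one that stands for engagement?

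*Combined protocol and SAP*

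**What the plan says.** The abstract promises more than the primary endpoint: "The impact of the intervention on secondary outcomes (e.g., engagement in the program) will also be assessed". Engagement also appears in the protocol title, "Facilitating Emerging Adult Engagement in Evidence-Based Treatment for Early Psychosis through Peer-Delivered Decision Support Part 2".

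Section 11 e) (Study Endpoints) lists 15 secondary measures and labels them exploratory. Two bear directly on engagement. The Intent to Attend Measure records participants' "intention to engage in the coordinate specialty care program". The Service Engagement Scale is described as "A clinician-rated scale that measures engagement in community mental health services". Several scales are described as having parts. The Recovery Assessment Scale entry reads "This scale measures personal recovery and consists of 5 factors", and the Working Alliance Inventory is assessed "in three domains: agreement on goals, assignment of tasks, and the development of bonds".

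The method is given in two places. Section 11 f) (Data Management) has the general rule: "To examine within-group differences in quantitative measures pre- and post-intervention, we will conduct paired samples t-tests". The SAP narrows this for the primary measure: "we will conduct a paired samples t-test using DCS Factors Contributing to Uncertainty subscale scores". Beyond that, the SAP's quantitative content is descriptive summaries and 95% confidence intervals for estimates. It mentions no secondary measure.

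**The concern.** For the primary measure the SAP goes down to subscale level. For the other 13 repeated measures it is silent, and the protocol's rule says only that quantitative measures get paired t-tests. Three choices are therefore left to the analyst:

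- whether a scale with several parts is tested as a total, by part, or both;
- which scale carries the abstract's claim about engagement;
- which items of the service-use form (SURF-M), which mixes inpatient care, outpatient care and medication, are analysed at all.

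The worry is selective emphasis. With two engagement scales and neither designated, an author could feature whichever one moved. Section 14 says results will be posted together with the protocol and SAP, and a reader of that posting could not tell which scale was planned. The SAP says findings will shape a later R01 study, so a chance signal might be carried forward.

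**Working it through.** **Which measures the rule covers.** Table 1 marks 14 measures at both baseline and post-intervention. Removing the DCS leaves 14 − 1 = 13: perceived social support, control preference, perceived involvement in care, insight, recovery, internalized stigma, empowerment, decision self-efficacy, SURF-M, adherence, intent to attend, service engagement and working alliance. The other two of the 15 secondary measures (Intentional Peer Support, Satisfaction with Decision) are post-intervention only, so no pre/post test applies. The rule and the table thus identify every measure and give it a method. Only the score is open.

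**How many tests the rule could mean.** Section 11 e) describes parts for five of the 13: social support 3, involvement 3, insight 3, recovery 5, working alliance 3, which sum to 17. The other 8 are counted at one score each. This is a judgement: the empowerment scale's description could also be read as listing parts.

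| Reading | Tests | Expected p<0.05 if nothing changes |
|---|---|---|
| One score per measure | 13 | 0.05 × 13 = 0.65 |
| Parts replace totals | 8 + 17 = 25 | 0.05 × 25 = 1.25 |
| Parts and totals | 25 + 5 = 30 | 0.05 × 30 = 1.50 |

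The documents state no significance level, so 5% is assumed. If the tests were independent, the chance of at least one false positive would be 1 − 0.95^m, which is 0.487, 0.723 and 0.785 for m = 13, 25 and 30. Correlated scales would give less. Even the leanest reading leaves about an even chance under independence, so a list of scores would not make isolated p-values here trustworthy.

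**The two engagement scales.** Assume normal change scores, 12 to 20 complete pairs, and a correlation of 0.3 to 0.7 between the two changes. By simulation, if both scales truly change by 0.5 SD, the two t-tests fall on opposite sides of p = 0.05 in 25–41% of studies; at 0.3 SD, in 16–32%. If neither changes, at least one is significant in 8–10%.

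The source of the disagreement is visible at n = 20 with correlation 0.3. Each test has about 56% power at 0.5 SD, and P(disagree) = 2 × (power − P(both significant)) = 0.41, so P(both significant) is about 0.56 − 0.205 = 0.355. Low power drives the figure. Designating one scale leaves it as it is.

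**What the estimates can show.** The 95% interval for a mean change has half-width t(0.975, n−1)/√n in SD units: 2.093/√20 = 0.47 at n = 20 and 2.201/√12 = 0.64 at n = 12. Either engagement result will be imprecise, and the intervals the SAP already requires will show it.

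**Which scale fits the abstract.** The abstract speaks of the program. The Intent to Attend Measure refers to that program but records intention. The Service Engagement Scale is rated by clinicians but is described in terms of community services generally. The text does not settle the choice, and an outside reviewer has no basis for imposing one.

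**SURF-M.** Section 11 f) already gives frequencies and percentages for yes/no variables, which suits any-use items. The documents give no rate of service use, so any figure for how badly a t-test would behave on days or contacts would rest on invented inputs.

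**The case for a change.** The strongest case for a change is that an exploratory label excuses low power and the lack of multiplicity control, but does not say which score answers an aim stated in the abstract and reflected in the title. The SAP shows it can name a score, since it does so for the DCS. A short table would need no new data or visits and would let a reader of the posted documents check what was planned.

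Much of that is true. No score is named, no engagement outcome is designated, and a table would cost little. It would also do little. Intervals are already planned. The descriptive rule already handles yes/no service-use items. Testing totals only assumes that every instrument has a total, which the documents do not establish (the Control Preference Scale and the adherence scale are examples). The general rule takes in both engagement scales, so applying it as written produces both results, and nothing in the plan suggests one would be withheld. The hypotheses in section 6 concern decision-making needs, feasibility and acceptability. Engagement enters the abstract only as an example of a secondary outcome.

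**Conclusion.** The plan leaves detail out, but the omission does not make an analysis wrong or impossible. All 13 measures have a method from section 11 f) read with Table 1, and the choice of score is one that analysts can make sensibly from each instrument's own scoring. The consequence is confined to exploratory results in a single-group pilot whose size of 20 was set on practical grounds (section 9). The DCS analysis is unaffected.

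The possible cost is 0.65 to 1.5 expected chance findings, depending on how the rule is read, and a 25–41% chance that the two engagement tests disagree when both effects are 0.5 SD. The first figure assumes a 5% level. The second also assumes normal changes, 12–20 pairs and correlations of 0.3–0.7. Naming a single engagement scale would not lower the second figure. This conclusion assumes that both engagement scales are reported, as the general rule implies, and that the secondary results are presented as exploratory. On that footing the plan can stand as written.
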